#### 8.5. Record Retention

The clinical data generated at the dialysis facility is retained at the data warehouse of the dialysis provider organization in accordance with each organizations standard operating procedures. The trial database at the University of Pennsylvania will be maintained for a period of 5 years following completion of the study, after which it will be archived. A copy of the data will be transferred to the NIDDK data repository in accordance with NIDDK policy. Data elements that are unique to one of the dialysis provider organizations, infrequent values, or any other elements that have potential for identifying provider organization, dialysis facility, or participant will not be included in the reposited data.

# **STATISTICAL ANALYSIS PLAN**

## Version 1.1

Prepared By:Senior Biostatistical Scientist and the Data Coordinating Center
Center for Clinical Epidemiology and Biostatistics (CCEB)
[name]
Perelman School of Medicine at the University of Pennsylvania
[name]

Protocol Summary		
Title	Time to Reduce Mortality in End-Stage Renal Disease (TiME) Trial	
Short Title	TiME Trial	
Protocol Number	817911	
Sponsor	National Institutes of Health: NIDDK, Office of the Director	
Design	Cluster-randomized, open label, pragmatic clinical trial	
Principal Investigator	[name], M. D.	
Objectives	
 
To determine whether dialysis facility implementation of a minimum hemodialysis session duration of 4.25 hours (versus usual care) for patients with end-stage renal disease initiating treatment with thrice weekly maintenance hemodialysis has benefits on mortality, hospitalizations and health-related quality of life.
 
To demonstrate the capacity to conduct a large, pragmatic clinical trial in partnership with two large dialysis provider organizations.
 
	
Intervention	Intervention facilities will recommend a minimum hemodialysis session duration of 4.25 hours. Control facilities ("Usual Care") will not implement a trial-driven recommendation about dialysis session duration.	
Enrollment Period	3 years	
Duration	4.5 years	
Study Center(s)	Dialysis facilities operated by DaVita and Fresenius Medical Care, two large dialysis provider organizations	
Data Coordinating Center	Clinical Research Computing Unit, Center for Clinical Epidemiology and Biostatistics, University of Pennsylvania Perelman School of Medicine	
Number of Facilities & Patients	402 dialysis units	
	6880 patients	
Main Eligibility Criteria	Dialysis Facility Eligibility	
	
 
Willingness of the facility's Medical Director, nephrologists and clinical leadership to adopt a facility approach of prescribing dialysis sessions of at least 4.25 hours for patients initiating treatment with maintenance hemodialysis (incident patients).
 
	
	
 
Capacity to accommodate treatment session durations of at least
 
4.25 hours for incident patients.
 
	
	3. Facility use of the electronic data systems of the dialysis provider organization.	

Protocol Summary			
	Patient Eligibility		
	Inclusion Criteria		
	1. Initiation of maintenance dialysis within the past 120 days.		
	2. Treatment with maintenance dialysis in a participating facility.		
	3. Age ≥18 years.		
	Exclusion Criteria		
	
 
Unwillingness to participate. Patients receiving dialysis in facilities in the Intervention arm can participate without agreeing to a minimum dialysis session duration of 4.25 hours. Data collection for such participants will be identical to those who receive the session duration of ≥4.25 hours.
 
Patients who are unable to provide consent for dialysis care will be avaluated from trial participants.
 
		
Outcomes	excluded from trial participation.		
Outcomes	Primary Outcome: death Major Secondary Outcomes: hospitalizations, health-related quality of life		
Duration of intervention	Up to 3 years		
Analytic Approach	
 
Primary outcome: intention to treat comparison of time to death between Intervention and Usual Care groups.
 
		
	Analysis will include generation of the hazard ratio and 95% confidence interval for the intervention. Significance testing will be performed with two-tailed p values of ≤ 0.05 considered significant. Survival curves with 95% confidence intervals will be generated using the Kaplan-Meier method. Secondary analyses will incorporate adjustment for co-variables that are not balanced between randomization groups.		
	2. Secondary outcomes:		
	
 
a) comparison of hospitalization rates between Intervention and Usual Care groups
 
		
	
 
b) comparison of change over time in KDQOL™36 domains between Intervention and Usual Care groups
 
		
	3. Primary analysis population : patients with anthropometric volume ≤ 42.5 liters. Referred to as "Primary Treatment Assessment Population."		
	4. Secondary analysis population : all patients. Referred to as "Extended Analysis Population."		
Study Oversight	An independent Data and Safety Monitoring Board (DSMB) appointed by NIH will review trial progress, data quality, and interim analyses throughout the course of the trial in accordance with a Data and Safety Monitoring Plan.		

#### **1** STUDY DESIGN

The TiME Trial is a cluster-randomized, parallel-group pragmatic clinical trial for patients initiating treatment with maintenance hemodialysis. The trial is one of the pragmatic trial demonstration projects of the National Institutes of Health (NIH) Health Care Systems Research Collaboratory. The trial will be conducted in partnership with DaVita and Fresenius Medical Care, the two largest dialysis providers in the United States who together care for approximately 70% of the US dialysis population.

The primary objective of the TiME Trial is to determine whether, compared with usual care, dialysis facility implementation of a minimum hemodialysis session duration of 4.25 hours for patients with end-stage renal disease initiating treatment with thrice-weekly maintenance hemodialysis improves clinical outcomes including survival. The secondary objective is to demonstrate the feasibility of conducting a large, pragmatic clinical trial in partnership with two large dialysis provider organizations.

Participating dialysis units will be randomized to the Intervention group or the Usual Care group. Intervention facilities will adopt an approach of recommending dialysis session durations of at least 4 hours and 15 minutes (255 minutes) for eligible patients. Usual Care facilities will have no trial-driven approach to dialysis session duration. The trial will use an opt-out approach to participation in which all eligible patients initiating dialysis in participating facilities will be enrolled unless they opt out of allowing their clinical data to be included in the trial dataset.

Four hundred and two dialysis facilities will be randomized in a 1:1 distribution to the Intervention arm or the Usual Care arm. Facilities randomized to the Intervention arm will adopt the practice of recommending dialysis session durations of at least 4.25 hours for all patients initiating hemodialysis treatment regardless of body size or dialysis solute clearance measurements. Facilities randomized to Usual Care will have no trial-driven approach to dialysis session duration. Participants will be followed for up to 3 years. The primary endpoint is mortality; major secondary endpoints are hospitalization rate and quality of life. Secondary outcomes include hospitalization rates compared between treatment groups; health related quality of life (HRQOL) utilizing the kidney disease-specific questionnaire KDQL™36; and other secondary effectiveness outcomes such as pre-dialysis blood pressure, post-dialysis blood pressure, inter-dialytic weight gain, and dialysis attendance compared between treatment groups.

Pragmatic features of the TiME Trial include 1) high generalizability due to non-restrictive eligibility criteria and broad representation of participating facilities, 2) implementation of the intervention by clinical care providers rather than by research personnel, and 3) complete reliance on data obtained through routine clinical care rather than through research activities. The source of outcomes data will be the electronic data systems of the dialysis provider organizations.

#### 2 DATA ACQUISITION, MANAGEMENT, AND APPROACH TO REPORTING

#### 2.1 Data Acquisition

Facility and patient enrollment at the two dialysis provider organizations will be monitored by the Data Coordinating Center (DCC) at the University of Pennsylvania. The DCC has established a data transfer process with each dialysis provider organization in which pre-specified data elements will be extracted from the clinical data systems of the dialysis provider organizations by their information technology personnel. After internal data quality assessment, the data will be transferred electronically to the Data Coordinating Center once per month. The transfer of data will be cumulative rather than incremental – i.e., all trial data accumulated to date will be transmitted rather than only newly acquired data since the prior data transfer. Each month the DCC will combine the uploaded data from the two dialysis provider organizations into a single trial database and reviewed the data for completeness and implausible values. Reports will be generated and shared with the dialysis provider organizations and the Steering Committee to allow regular monitoring of adherence to the Intervention.

#### 2.2 Session Duration

Because the trial relies on existing clinical data, the ability to query the dialysis providers for individual data elements is limited. The DCC will use the following approach for managing and validating session data for reporting.

- a. Reports of session duration exclude single dialysis sessions < 60 minutes in duration since these represent aborted sessions.
- b. Two dialysis sessions occurring on the same date are treated as a single session that was interrupted and resumed. The time records will be summed.
- c. When a pre-session dialysis record does not have a corresponding post-session record, it is treated as a session that was never initiated and the session is excluded from summary reports.

#### 2.3 Missed Dialysis Sessions

A missed dialysis sessions is defined as a session that is missed despite the expectation that it would occur. The estimated missed sessions per month estimate how many sessions a participant has missed not attributable to hospitalization. The process for determining skipped sessions is as follows:

a. Expected number of dialysis sessions per day: The TiME Trial enrolls participants who are prescribed thrice weekly dialysis sessions and thus the number of expected dialysis sessions per week is 3/7. In practice, the prescribed frequency occasionally changes, usually temporarily. Therefore, the expected number of dialysis sessions per day takes into account the prescribed frequency.

- b. Number of observed days in a week: For participants without hospitalization, this number is always 7. If a participant is hospitalized for x number of days in a week, the number of observed days in the week will be (7 x). The reason that the hospitalized days are removed is because participants receive dialysis during the hospitalization but the session data are not included in the dialysis provider clinical data and thus are not in the trial dataset.
- c. Expected number of dialysis sessions in a week: This is calculated by multiplying the expected number of dialysis sessions per day by the number of observed days in a week.
- d. Number of missed sessions in a week: For each participant, the number of missed sessions for each week is calculated by subtracting the number of delivered dialysis sessions from the expected number of dialysis sessions in that week.
- e. Total number of missed sessions: For each participant, the total number of missed sessions is calculated by summing numbers of missed sessions in all weeks.
- f. Gaps in dialysis session data are compared to hospitalization information [admission and discharge dates] in order to determine reason for missing session data.

#### 2.4 Status Changes

The two dialysis provider organizations have different methods for identifying and recording patient status changes. Throughout the course of dialysis, participants may have experienced multiple events of status change. For the purpose of the statistical analyses, only the current event of status change will be considered. Events of status change happened prior to any dialysis session will not be considered as the event of status change; i.e., only the event of status change resulting in no dialysis data transferring to DCC will be considered. As a result we have examined and consolidated all of the information transmitted into the following status change categories to represent each participant's current status:

Participant Status Categories	Details
Study cutoff	Alive
Death	
Modality change	To peritoneal dialysis, to other modality
Loss-to-follow-up	Prison/Abroad, became ineligible, hospitalized, Termination/loss-to-follow-up/opt-out, Recovery, Transfer to a facility outside of the dialysis provider organization
Transplantation	
Transfer to a non-participating facility within the dialysis provider organization	

#### **3** INTERIM ANALYSES FOR THE DATA AND SAFETY MONITORING BOARD

The protocol includes a plan for an interim efficacy analysis when the participants reach 50% information time to be provided to the DSMB. To avoid inflating the overall Type I error rate for the primary analysis of effectiveness, an O'Brien-Fleming boundary will be used to calculate the nominal significance level to which the interim p-value is compared. The DSMB will have the authority to recommend that the trial be stopped early based on efficacy, futility, or safety concerns.

#### 3.1 DSMB-Requested Interim Analysis

A mid-course interim analysis, including a futility analysis, was requested by the DSMB. The interim analysis was conducted using data through October 2016 when the information time was approximately 50%. The following plan was provided to the DSMB before the interim efficacy analysis and the futility analysis were conducted:

The TiME Trial design provides 80% power to detect a hazard ratio of 0.85 from a Cox proportional hazards model at a type 1 error rate of 5%. To account for the interim analysis of accumulated data in the TiME Trial, the Lan-DeMets alpha spending function method will be used to determine the O'Brien-Fleming boundary to maintain an overall type 1 error rate of 5%. All confidence intervals will be adjusted for the interim analysis with one-look at information time of 50% (i.e., the O'Brien-Fleming boundary for a two-sided test would be {-2.96, 2.96}). In other words, the null hypothesis that the hazard ratio equals 1 would be rejected if the test statistic is less than -2.96.

#### 4 FINAL DATA ANALYSIS UPON COMPLETION OF TRIAL

#### 4.1 General Approach

Upon completion of the trial, after all data has been entered in the database and query resolution is complete, description of the data and the primary statistical analysis will be performed. The DCC will produce a final report outlining all analyses and interpretation of the results. The report will be used as the basis of the primary results manuscript to be prepared for publication. Details of the analyses and statistical methods to be included in the final report are outlined in this Statistical Analysis Plan. All statistical tests described will be conducted using a two-sided level of significance.

Before proceeding with inferential analyses, the data for this study will be fully described. Data will be examined for the primary outcome and all covariates to assess distributional assumptions, and balance of covariates among the study arms.

In this normal theory framework, we will first test for any difference between the trial arms, using a multivariable linear model. The multivariable model will be implemented where the interest is on testing the two arms using a Wald test. The assessment of the primary hypothesis of no difference between the arms will be conducted using a two-sided test.

Since randomization will be implemented at the site level, the intra-cluster correlation will be addressed in the models for all analyses. The design factors, stratification on each site's racial distribution (black vs non-black) and catheter use, not included in the primary analysis will be assessed in secondary analyses.

#### 4.2 Baseline Data

Descriptive statistics will be used to summarize baseline characteristics both in overall and in each treatment arm. Summary statistics such as means, standard deviations, medians and interquartile ranges will be produced for all continuous variables. Frequencies and percentages will be computed for all categorical and ordinal variables. Graphical methods including density plots, histograms, and boxplots will be used to examine distributions, identify potential influential points, and guide in the choice of transformations, if warranted. The balance of baseline measures across the two treatment arms will be compared with robust variance estimate to take in account the clustering effect.

#### 4.3 Primary Efficacy Analysis

The primary outcome is time to death and the primary efficacy analyses will be an intention-to-treat (ITT) analysis on mortality for the primary analysis population, referred to as "Watson ≤ 42.5L". Each participant will be included in the arm in which her/his dialysis facility was randomized, regardless of adherence to the assigned strategy. The analysis will be performed using Cox proportional hazards models to compare the hazard rates between the Intervention and Usual Care arms. Intra-cluster correlation (ICC) between participants within the same facility will be modeled by using a random component for the hazard function (i.e. frailty models). The hazard ratio (HR) for mortality between Intervention and Usual Care arms will be reported by calculating the exponential function of the estimated parameter of the treatment effect from the Cox models. The test statistic will be calculated to test the null hypothesis that the hazard ratio equals 1 versus the 2-sided alternative hypothesis that the hazard ratio is greater than and/or less than 1. To examine the proportionality between the Intervention group and the Usual Care group, an interaction term between treatment and a function of time will be included in the model; i.e., to determine whether the treatment effect on mortality varies as a function of time that a participant has been under the treatment. The same approach will be used for the primary outcome analysis for the extended analysis population (all participants regardless of Watson V) as well as in the stratified analyses and the large-size subgroup of participants, referred to as "Watson >42.5L".

#### 4.4 Secondary Analyses of the Primary Outcome

#### 4.4.1 Stratified Analyses

Secondary analyses of the primary outcome of mortality will include stratified analyses 1) participant's self-identified race (black, non-black); and 2) participant's use of a central venous catheter at baseline (yes, no).

In addition, interaction terms between treatment and body size and treatment and sex will be considered to determine whether treatment effects differ by body size or sex subgroups.

#### 4.4.2 Exploratory As-Treated Analyses

#### 4.4.2.1 Rationale

Non-adherence to the trial intervention is one of the most common factors complicating the application of causal inference to results from randomized trials. This is particularly the case for pragmatic trials, where the biological effect of the treatment received may differ greatly from the effectiveness of the intervention as estimated using intent-to-treat analyses. While the primary analyses will be performed using standard intent-to-treat approaches to estimate effectiveness, additional explanatory analyses using modern methods of causal inference will be performed to assess the biological effect of the treatment received; i.e., as-treated analyses.

Non-adherence to the TiME trial intervention may occur as a result of unwillingness by patients to undergo longer dialysis sessions, preference of the treating nephrologist to prescribe shorter sessions for specific patients, operational barriers for facilities, and patient transfer to non-participating facilities. Adherence information for participants will be collected during the entire follow-up period in the form of the both prescribed and delivered duration of each dialysis session and relevant timeupdated covariates.

To monitor patient adherence, we use an aggregated metric, average session duration within each patient, as well as a graphical tool, lasagna plot, at session-level for each patient. In the as-treated analysis, we will use the previously described Cox models with frailty to investigate the effect of session duration (prescribed and delivered) on mortality rate.

One disadvantage of the as-treated analysis for mortality is that, for example, a difference in mortality for a 30-minute increase in delivered session duration is potentially confounded by unmeasured confounders (e.g. healthier patients may be more likely than sicker patients to have longer sessions). Therefore, the difference in mortality in such an analysis infers association, but not necessarily causation; or, equivalently, it is a result from an observational study, not a randomized trial. An advantage of the TiME Trial is its randomization. Consequently, we will conduct instrumental variable (IV) analyses using the randomization assignment as an instrument. The property of the instrument (randomization) is to provide a proper way to adjust for the unmeasured confounders (e.g. indication bias), and to provide a causal interpretation of the difference in mortality for a 30-minute increase in delivered session duration among compliers (those patients who, because of the randomization, increase their dialysis session duration from x minutes to x+30 minutes). Although the strength of the instrument within an IV analysis may be determined by the separation in delivered session duration between Intervention and Usual Care arms (which will be decreased by non-adherence), this will oaffect the precision of the causal interpretation (i.e. unbiased hazard ratio).

#### 4.5 Secondary Outcomes

Secondary outcomes include hospitalization rates using data collected during the follow-up period, pre- and post-dialysis blood pressure using data from each dialysis session, and ultra-filtration rate calculated using data from each dialysis session, laboratory data measured every month, and quality of life measured approximately annually. Analyses of the secondary outcomes will be performed for the primary analysis population (Watson V  $\leq$ 42.5L), for the extended analysis population (all participants regardless of Watson V), and for the subgroup of participants with Watson V >42.5L, as well as in the stratified analyses.

#### 4.5.1 Hospitalizations

Hospitalization data will be analyzed in two ways. First, time to the first hospitalization will be compared between treatment groups using multivariable Cox proportional hazards models adjusting for clustering. Second, to compare the hospitalization rates between treatment groups, a generalized estimating equations (GEE) approach will be used assuming a Poisson distribution with an offset term to account for the length of follow-up for each participant and an independent correlation structure to account for participants within the same facility. Similar to the analyses of the primary endpoint, analyses will be performed for the primary treatment assessment population and the extended analysis population.

#### 4.5.2 Quality of Life

Quality of life as assessed by the Kidney Disease Quality of Life Short Form-36 (KDQOL 36™), a kidney disease specific instrument administered by both dialysis provider organizations at least once per year as part of routine practice and in accordance with CMS requirements. The KDQOL consists of five

sub-domains: SF12 physical scores, SF12 mental scores, burden of kidney diseases scores, symptoms/problems scores and effects of kidney diseases scores. For each sub-domain, the baseline measurement is determined by the average of all available measurements collected between 90 days before and 120 days after the date of the first transferred dialysis session; and the follow-up measurement is determined by the average of all available measurements collected beyond 120 days after the first transferred dialysis session; and the follow-up measurement is determined by the average of all available measurements collected beyond 120 days after the first transferred dialysis session. Changes in the KDQOL sub-domains between treatment arms will be compared using linear mixed effects models to account for participants within the same facility.

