# 4.7.2.2. Health-Related Quality of Life (HRQOL)

Quality of life is an important secondary outcome of the TiME Trial. The trial hypothesis is that extension of treatment time will improve hemodynamic stability during dialysis and increase solute clearance, and that these effects will lead to improvement in physical aspects of health-related quality of life. The HRQOL questionnaire used for the TiME Trial will be the KDQOL™36, a kidney disease-specific instrument that is administered by both dialysis provider organizations to all patients as part of routine practice and in accordance with the CMS requirement that quality of life be assessed at least once per year. The investigator team considered other QOL instruments and decided, based in part on logistical advantages, to use the survey that is already being administered as part of routine care delivery at the dialysis facilities.

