population), assuming an ICC of 0.03. With this sample size the trial will also have 80% power to detect a HR of 0.88 in the extended population with a two-sided alpha level of 0.05.

Hazard Ratio	Intra-class Correlation Coefficient	Number of Dialysis Facilities	Sample Size for Primary Assessment Population	Total Sample Size
0.9	0.04	1038	10380	16608
	0.03	970	9700	15520
	0.02	902	9000	14432
0.85	0.04	432	4320	6912
	0.03	402	4020	6432
	0.02	374	3740	5984
0.8	0.04	230	2300	3680
	0.03	216	2160	3456
	0.02	200	2000	3200

Table 2.	Sample Size	Requirement
----------	-------------	-------------

For the secondary outcome of hospitalization, a hospitalization rate of at least one per patient per year is expected. Conservatively estimating the minimum detectable effect size using only the first hospitalization, and assuming an ICC of 0.03, the study has 80% power to detect a hospitalization risk ratio of 0.90 in the primary treatment assessment population and 0.92 in the extended population. For the quality of life outcome, estimating, based on data from the HEMO trial, that the standard deviation of the change of the Physical Health Composite is approximately 10 units from baseline to year one, and assuming that 50% of the participants will complete the KDQOL™36, the study has 80% power to detect a difference of 1.4 for the change in the physical composite score (PCS) or mental composite score (MCS) in the primary efficacy population and a mean difference of 1.1 in the extended population. In repeated measures analyses, the actual minimum detectable effect size will be even smaller because quality of life will be assessed once per year during the follow-up period.

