#### **Analyses of Secondary Endpoints**

Several secondary analyses will be conducted, both to evaluate the secondary outcomes and to supplement the primary endpoint comparison. Secondary outcomes include hospitalization data collected during the follow-up period and quality of life measured every year. Generalized estimating equations (GEE) will be used to model repeated quality of life data. GEE can account for the correlation of repeated measures within subject and also the correlation of repeated measures within cluster. Hospitalization data will also be analyzed using a GEE approach assuming a Poisson distribution with an offset term to account for the length of follow-up for each participant.

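### The SAP's quality-of-life change score needs a KDQOL survey by day 120, but routine surveys are required only yearly, and no rule says how participants without a baseline are analysed

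*Combined protocol and SAP*

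**What the plan says.** SAP 4.5.2 defines two values per participant and sub-domain. Baseline is "the average of all available measurements collected between 90 days before and 120 days after the date of the first transferred dialysis session". Follow-up is "the average of all available measurements collected beyond 120 days after the first transferred dialysis session". The comparison is then: "Changes in the KDQOL sub-domains between treatment arms will be compared using linear mixed effects models to account for participants within the same facility".

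No survey is done for the trial. SAP 4.5.2 describes the instrument as "administered by both dialysis provider organizations at least once per year as part of routine practice", and protocol 4.7.2.2 cites "the CMS requirement that quality of life be assessed at least once per year". Protocol 4.8 lists the KDQOL scores as collected annually. Nothing schedules a survey at entry or within the first 120 days.

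Protocol 6.3 describes a different model: "Generalized estimating equations (GEE) will be used to model repeated quality of life data". Protocol 6.2 gives a detectable difference of 1.4 points in the primary population and 1.1 in the extended population, with an SD of change of 10 and "assuming that 50% of the participants will complete the KDQOL". It adds that repeated-measures analysis would make the detectable difference smaller still.

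Protocol 6.4 and SAP 5 expect missing quality-of-life data, including from uncompleted questionnaires. The strategies they name are for loss to follow-up and for death.

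**The concern.** A first survey on, say, day 200 meets the yearly requirement. It supplies a follow-up value and no baseline, so no change can be formed, however many later surveys the participant completes. The quality-of-life model names clustering by facility only, whereas the blood pressure and ultrafiltration models (SAP 4.5.4 and 4.5.5) also account for repeated measurements on the same person. That contrast points to one change score per participant, which leaves no place for someone with follow-up surveys alone.

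Such a participant is alive and under observation, so is neither lost to follow-up nor dead. Inverse probability weighting would reweight those who have a score; it would not bring back those who do not. Quality of life is a major secondary outcome and is listed within the primary objective (protocol 2.1), so unused surveys and an uncertain power statement matter.

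**Working it through.** **Reproducing the plan's figure.** Inputs from protocol 6.2: SD 10; 4020 participants in the primary population and 6432 in all; 402 facilities; mean cluster size 10 (primary) or 16 (all); 50% completion; 80% power. Two assumptions are needed, because 6.2 does not state these values for quality of life: two-sided alpha 0.05, and an ICC of 0.03 (given for mortality and hospitalization). With n analysed participants split 1:1,

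MDD = (1.960 + 0.842) × 10 × √(4 × DE / n), DE = 1 + (m − 1) × 0.03.

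- Primary, n = 4020 × 0.5 = 2010. Full cluster size m = 10: DE = 1.27, MDD = 1.41. Analysed cluster size m = 5: DE = 1.12, MDD = 1.32.
- Extended, n = 6432 × 0.5 = 3216. m = 16: DE = 1.45, MDD = 1.19. m = 8: DE = 1.21, MDD = 1.09.

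The stated 1.4 and 1.1 are both reproduced to rounding, though under different cluster-size conventions. Both conventions are carried forward.

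**Share with a baseline (assumed, not in the documents).**

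- If all patients are surveyed near entry: 100% have a baseline, none affected.
- If first-survey timing is uniform over 365 days and the whole window counts (90 + 120 = 210 days): 210/365 = 58% have a baseline, 42% do not.
- If it is uniform and only the 120 days after the first transferred session count: 120/365 = 33% have a baseline, 67% do not.

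**Effect if the 50% already means both surveys.** n stays at 2010 and 3216, so 1.4 and 1.1 stand.

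**Effect if the loss comes on top of 50% completion.** The lower end of each range uses the analysed cluster size (n/402), the upper end the full cluster size.

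- Primary, 58%: n = 2010 × 210/365 ≈ 1156, MDD 1.69–1.86, power at 1.4 of 64–56%.
- Primary, 33%: n = 2010 × 120/365 ≈ 660, MDD 2.20–2.46, power at 1.4 of 43–36%.
- Extended, 58%: n ≈ 1850, MDD 1.37–1.57.
- Extended, 33%: n ≈ 1057, MDD 1.76–2.07.

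With the revised counts of protocol 6.2.1 (4250 in 256 facilities) and the same ICC, the primary-population ranges are 1.69–1.94 and 2.17–2.57, so the picture is unchanged.

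**The case against.** The strongest reply is that the SAP never says participants without a baseline are excluded, so the flaw is an unstated rule rather than a stated exclusion. That is right. A reader might infer that the SAP discards these surveys; the text only makes that the likeliest reading. Likewise, protocol 6.3 does not say whether its GEE models raw scores or changes, and the Protocol Summary speaks of change over time. So the GEE could use follow-up-only participants; it is not shown that it would.

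The second reply concerns size, and most of it stands. Once a year is a minimum, so early surveys may be common. The figure of 33% is a floor under uniform timing: it ignores the 90 days before the first transferred session. It also ignores that patients may enter up to 120 days after starting dialysis. If the first transferred session is at entry (assumed), entry on dialysis day 60 gives (60 + 120)/365 = 49%. The 50% completion appears in a sentence about change from baseline to year one, so it may already mean both surveys. If timing were the only loss, 58% would give n = 4020 × 210/365 ≈ 2313 and, with m = 2313/402 ≈ 5.75 and DE ≈ 1.14, an MDD of about 1.25, below the stated 1.4. The inference that power must be badly reduced is therefore not supported.

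A reader might also infer that open-label facilities would time surveys differently by arm. No passage suggests this; it is a possibility that counts by arm would reveal.

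What the reply does not remove is the gap itself: no text says how a participant with follow-up surveys and no baseline is handled.

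**Conclusion.** The point holds as a gap in SAP 4.5.2 that should be closed. The change-score definition leaves participants first surveyed after day 120 without a score, and the named missing-data strategies do not restore them.

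The number affected is unknown: nil with surveys near entry, about 42–67% under the assumed uniform timing. The consequence for the primary population runs from none (1.4 stands if 50% means both surveys) to a detectable difference of roughly 1.7–2.5 if the loss is added to 50% completion. That upper range rests on the uniform-timing assumption, on adding the two losses together, and on applying the mortality ICC of 0.03 to quality of life. The documents establish none of these three.

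**What to change.** In SAP 4.5.2, make the main analysis a longitudinal model on all individual survey scores by actual survey date: either the protocol's GEE or a mixed model with random facility and participant effects. Participants with only baseline or only follow-up surveys then contribute. The present window already requires survey timing to be known, so no new data are needed.

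Do not constrain the arms to equal means over the whole window to day 120. That window reaches 120 days past the first transferred session, when session lengths may already differ by arm, and patients enrol after their facility is randomized, with an opt-out. An equality constraint should apply at most at the first session, as a sensitivity analysis.

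Report by arm the numbers with baseline only, follow-up only and both. Keep the change score as a supportive analysis. In protocol 6.2, state whether the 50% refers to one survey or both.

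The cost is SAP wording and slightly more modelling. The mixed model relies on data being missing at random given the observed scores and covariates. An unweighted GEE needs a stricter condition, so if GEE is chosen, the inverse probability weighting already planned should be specified for survey non-completion as well.
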